### **5.6.2 Assessment of Compliance**

The IMP will be administered to the patient by authorized trial staff at the trial sites.

Overdoses and medication errors with and without clinical consequences must be reported as adverse events (Section 8.1). In presence of clinical reactions these must be reported as separate adverse events. In absence of clinical reactions this must be specified (Section 8.2.2).

### **5.7 Auxiliary Supplies**

The Sponsor will provide the trial sites with needles, and other auxiliaries needed for preparation and administration of the IMP.

### **5.8 Return and Destruction of Medicinal Products and Auxiliary Supplies**

All used IMP is to be destroyed at the trial site in accordance with local legislation after the drug accountability has been finalized and signed-off by the Investigator. If the IMP cannot be destroyed at the trial site it can be sent back to Warehouse/Sponsor after drug accountability has been finalized and signed-off by the Investigator.

All unused IMP will be returned for destruction, as instructed by the IMP Department at the Sponsor and in accordance with local requirements, after the drug accountability has been finalized.

## **6 TRIAL PROCEDURES**

### **6.1 Trial Flow Chart**

All patients must receive verbal and written information about the trial before entering the trial. Trial-related procedures must not be performed on a patient before the informed consent has been signed. The Investigator is obliged to keep logs of all screened and randomized patients. A flow chart of trial procedures and assessments per visit is provided in [Table 1](#) and a treatment flow chart is presented in [Table 2](#). All trial assessments are detailed in [Section 7](#).

**Table 1 Flow Chart of Assessments**

Visit number	Screening	Treatment / Follow-up Period												End-of-Treatment 	End-of-Trial
	1	2	3	4	5	6	7	8	9	10	11	12	13	14	
Month		0	1	2	3	4	5	6	7	8	9	10	11	12	
Days from Visit 2	Within 21 days prior to Visit 2	0	28	56	84	112	140	168	196	224	252	280	308	336	
Visit window (days)			±7	±7	±7	±7	±7	±7	±7	±7	±7	±7	±7	±7	
Signed informed consent a	X														
Inclusion/exclusion criteria	X	X													
Demographics	X														
Medical history	X														
CVD history	X														
██████████		X											X	X	
██████████		X											X	X	
██████████		X													
Height		X													
Physical examination	X												X	X	
History/stage/histology of prostate cancer/ECOG b	X														
- Radiographic imaging b, c	X												X	X	
Randomization		X													
Administration of IMP		--- See separate treatment flow chart (Table 2)---													
IPSS d		X			X			X			X			X	X
PRO e		X						X						X	X
Health economics f		X	X	X	X	X	X	X	X	X	X	X	X	X	X

Visit number	Screening	Treatment / Follow-up Period												End-of-Treatment 	End-of-Trial
	1	2	3	4	5	6	7	8	9	10	11	12	13		14
Month		0	1	2	3	4	5	6	7	8	9	10	11		12
Days from Visit 2	Within 21 days prior to Visit 2	0	28	56	84	112	140	168	196	224	252	280	308		336
Visit window (days)			±7	±7	±7	±7	±7	±7	±7	±7	±7	±7	±7		±7
12-lead ECG g		X	X					X						X	X
Vital signs (pulse and blood pressure) g	X	X	X	X	X	X	X	X	X	X	X	X	X	X	X
Blood sampling: g															
- Testosterone n	X		X					X						X	X m
- Clinical chemistry	X	X	X					X						X	X
- Hematology	X	X												X	X
- Glycemic evaluation h	X	X												X	X
- Metabolic evaluation i		X												X	X
- PSA	X	X			X			X			X			X	X m
██████████ l		X													
████████████████████ ██████████ l	X	X	X	X	X			X			X				X
Urine collection g	X	X												X	X
Drug accountability		X	X	X	X	X	X	X	X	X	X	X	X	X	X
Concomitant medication	X														
Changes in concomitant medication		X	X	X	X	X	X	X	X	X	X	X	X	X	X
Adverse events, including CV-related signs	X	X	X	X	X	X	X	X	X	X	X	X	X	X	X
End-of-Trial form															X

- a) Signed informed consent must be obtained prior to any trial-related procedure.
- b) Stage of prostate cancer should be based on clinical assessment and radiographic imaging (e.g. bone scan, MRI or CT performed as per standard clinical practice at the discretion of the Investigator) and should have been done within 3 months prior to randomization. If no radiographic image is available at the time of screening, a bone scan should be performed as part of the screening procedures. These data must be available for trial documentation before randomization.
- c) The bone scan at the End-of-Trial visit (or End-of-Treatment visit) as part of the PFS endpoint follow-up can be performed up to 7 days before the actual visit.
- d) The IPSS questionnaire should be completed by the patient before the PRO questionnaires DASI, CAQ and EQ-5D-5L.
- e) PRO questionnaires: 1) DASI, 2) CAQ, and 3) EQ-5D-5L. The questionnaires should be completed in the given order.
- f) Health economics: CV-related hospitalization events, CABG/PCI procedures and ER visit events.
- g) ECG, vital signs, blood sampling, and urine collection must be performed prior to dosing. The results from the Screening visit must be available prior to randomization.
- h) Glycemic evaluation at the Screening visit: HbA1c in all patients (fasting not needed). Glycemic evaluation at Visit 2 and at the End-of-Trial visit: plasma glucose and serum insulin. The blood samples must be taken while the patient is in fasting state, i.e. minimum of 8 hours without caloric intake.
- i) Metabolic evaluation: total cholesterol, HDL-cholesterol, low density lipoprotein LDL-cholesterol, triglycerides and uric acid. The blood samples must be taken while the patient is in fasting state, i.e. minimum of 8 hours without caloric intake.
- [REDACTED]
- [REDACTED]
- l) Patients who prematurely discontinue treatment with IMP, or receive prohibited medication (Section 4.3.2), should be called in for an end-of-treatment visit as soon as possible (within 30 days) after a decision of treatment discontinuation has been taken. Following the End-of-Treatment visit, the patient will be followed-up as described in Section 4.4.
- m) Blood sampling for analysis of testosterone and PSA should not be done in patients who have discontinued treatment with IMP and have performed an end-of-treatment visit.
- n) Due to diurnal variations in testosterone level, patients with a screening serum testosterone level <150 ng/dL can be re-tested with laboratory results available prior to randomization, at the discretion of the Investigator.

Abbreviations: CABG, Coronary Artery By-Pass Grafting; CAQ, Cardiac Anxiety Questionnaire; CT, Computed Tomography; CV, Cardiovascular; DASI, Duke Activity Status Index; ECG, electrocardiogram; ECOG, Eastern Cooperative Oncology Group; EQ-5D-5L, EuroQol Group 5 Dimensions 5 Levels Questionnaire; ER, emergency room; HbA1c, hemoglobin A1c (glycosylated hemoglobin); HDL, high density lipoprotein; [REDACTED] IMP, Investigational Medicinal Product; IPSS, International Prostate Symptom Score; LDL, low density lipoprotein; MRI, magnetic resonance imaging; [REDACTED] PCI, percutaneous coronary intervention; PFS, Progression-Free Survival; PRO Patient Reported Outcome; PSA, Prostate-Specific Antigen.

**Table 2 Treatment Flow Chart**

	Screening	Treatment/Follow-up Period												End-of-Trial
Visit number	1	2	3	4	5	6	7	8	9	10	11	12	13	14
Month		0	1	2	3	4	5	6	7	8	9	10	11	12
Days from Visit 2	Within 21 days prior to Visit 2		28	56	84	112	140	168	196	224	252	280	308	336
Treatment window		0	±7	±7	±7	±7	±7	±7	±7	±7	±7	±7	±7	±7
Degarelix group Degarelix, s.c. a		2x 120 mg	80 mg	80 mg	80 mg	80 mg	80 mg	80 mg	80 mg	80 mg	80 mg	80 mg	80 mg	
Leuprolide group Leuprolide, i.m. b		22.5 mg			22.5 mg			22.5 mg			22.5 mg			

a) Degarelix starting dose, Visit 2: two s.c. depot injections, each containing 120 mg of degarelix (i.e. the starting dose will be 240 mg). The volume of each injection is 3.0 mL.  
 Degarelix maintenance doses, Visits 3-13: a single s.c. depot injection containing 80 mg of degarelix. The volume of each injection is 4.0 mL.

b) Leuprolide patients: one leuprolide 22.5 mg 3-month depot injected i.m. according to label recommendations, every 3 months throughout the trial. The volume of each injection is 1.5 mL.

Abbreviations: i.m., intramuscular; s.c., subcutaneous.

## 6.2 Visit 1 (Screening)

Patients will be screened within 21 days prior to randomization for compliance with the inclusion and exclusion criteria.

The following must take place at Visit 1:

- Signed and dated written informed consent, obtained prior to any trial-related procedures
- Allocation of a screening number
- Check of inclusion and exclusion criteria (those which are possible to check at screening)
- Demographics (age, ethnicity, race)
- Collection of the following data:
  - Medical history
  - CVD history using Medical / CV History Request Form
- Vital signs (pulse and blood pressure)
- Physical examination
- History/stage/histology of prostate cancer should be based on clinical assessment and radiographic imaging. Bone scan (MRI or CT may be performed as per standard clinical practice at the discretion of the Investigator) should be performed within 3 months prior to randomization
- Blood collection for central laboratory analysis of (*Note*: The result must be available prior to randomization.):
  - Testosterone (Due to diurnal variations in testosterone level, patients with a screening serum testosterone level <150 ng/dL may be re-tested prior to randomization, at the discretion of the Investigator.)
  - PSA
  - Clinical chemistry and hematology parameters
  - HbA1c
-   

- Urinalysis (dipstick) (*Note*: The result must be available prior to randomization.)
- Recording of use of any concomitant medication (within the last 12 months prior to signed informed consent for participation in the trial)
- Adverse events, including CV-related signs

Patients considered eligible for the trial based on the inclusion and exclusion criteria assessed at this time point may proceed to the next visit (Visit 2).

### 6.3 Visit 2 (Month 0)

The following must take place prior to randomization:

- Ensure that the patient is still eligible for participation in the trial (including any changes in use of concomitant medications)
- Check those inclusion and exclusion criteria that were not possible to fully check during screening

Patients fulfilling all inclusion criteria and none of the exclusion criteria will proceed to randomization by an electronic system and thereby be allocated 1:1 (Section 4.2.2) to one of the two treatment groups.

The following must take place **after randomization, but before administration of the first dose of IMP (degarelix or leuprolide)**:

- IPSS
- PRO (DASI, CAQ and EQ-5D-5L)
- Health economics (CV-related hospitalization events, CABG/PCI procedures and ER visit events)
- Body measurements (body weight, waist and hip circumference, and height)
- [REDACTED]
- 12-lead electrocardiogram (ECG)
- Vital signs (pulse and blood pressure)
- Blood collection for central laboratory analysis of:
  - PSA
  - Clinical chemistry and hematology parameters
  - Glycemic and metabolic parameters (*Note*: The blood samples must be taken while the patient is in fasting state, i.e. minimum of 8 hours without caloric intake.)

■ [REDACTED]

■ [REDACTED]

[REDACTED]

- Urinalysis (dipstick)

Once the above has been completed, the following must be performed by the drug administrator:

- Dispense and administer IMP (degarelix or leuprolide) according to randomization and treatment flow chart (Table 2)
- Dispense anti-androgen therapy to metastatic patients randomized to receive leuprolide in cases where this is prescribed for flare protection, at the discretion of the Investigator.

Finally, the following must be recorded before the patient leaves the clinic:

- Drug accountability
- Adverse events, including CV-related signs

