### 3.5.3 Blinding

The feasibility process conducted by the Sponsor has demonstrated that a true double-blind design would be difficult to implement (due to different doses and treatment regimen and different incidence of injection-site reactions) and would be unlikely to fully maintain blinding through the randomized treatment administration period. Specific firewalls will be implemented between the sites, the Sponsor and the MACE assessors to minimize risk of bias. An external CEC Committee (Section 3.4.1) will be established for the trial to provide an independent and blinded adjudication of CV events. The CEC Committee will have coordinators who will work closely with the Sponsor team for the surveillance and query processes to identify all potential CV events from the clinical and safety databases and work collaboratively to redact information regarding the open-label trial treatment information for each endpoint. This team would assist with generating queries specific to each endpoint reported and would be fire-walled from the external CEC Committee physician reviewers that process the completed event packets for physician adjudication to ensure complete blinding of the adjudication team. The CEC classification and adjudication process are detailed in a separate CEC charter.

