#### 4.1.2 Exclusion Criteria

A patient who meets one or more of the following exclusion criteria cannot be included in this trial:

1. Previous or current hormonal management of prostate cancer (surgical castration or other hormonal manipulation, including GnRH receptor agonists, GnRH receptor antagonists, anti-androgens, estrogens, megestrol acetate, ketoconazole, abiraterone and enzalutamide); except neoadjuvant/adjuvant ADT (in this case treatment has to be terminated at least 12 months prior to randomization).
2. Hypersensitivity towards any component of the IMPs or excipients.
3. Uncontrolled type 1 or type 2 diabetes mellitus (defined as hemoglobin A1c [HbA1c]  $> 10\%$ ) at time of randomization.
4. Uncontrolled hypertension (systolic blood pressure  $> 180$  mmHg or diastolic blood pressure  $> 110$  mmHg) at time of randomization.
5. A history of congenital Long QT Syndrome or risk factors for Torsade de Pointes ventricular arrhythmias (e.g. heart failure, hypokalemia, concomitant medication known to cause QT prolongation).
6. Myocardial infarction within 30 days prior to randomization.
7. Stroke (hemorrhagic or ischemic) within 30 days prior to randomization.
8. Coronary, carotid, or peripheral artery revascularization within 30 days prior to randomization.

9. Planned or scheduled cardiac surgery or PCI procedure that is known at the time of randomization.
10. Other clinically significant disorder (other than prostate cancer and CVD) including, but not limited to, renal, hematological, gastrointestinal, endocrine, neurological, or psychiatric disease, and alcohol or drug abuse or any other condition, which may affect the patient's health or the outcome of the trial as judged by the Investigator.
11. Mental incapacity or language barrier precluding adequate understanding or co-operation.
12. Treatment with an investigational drug within the last month prior to randomization or longer if considered to possibly influence the outcome of the current trial or planned or concurrent participation in a clinical trial for any investigational drug or device.

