#### **4.2.2 Randomization**

Only patients who meet the eligibility criteria (Section 4.1) will be randomized to a treatment arm in this trial. The treatment arms will run in parallel.

Computer-generated randomization lists will be prepared centrally by the Sponsor's Department of Global Biometrics. Patients will be randomized to one of the two treatments in a 1:1 ratio stratified by baseline age group (<75 and ≥75 years of age) and region (North America and Other regions).

The patients will be randomized and allocated to a treatment through the eCRF and thereby receive a unique randomization number. The randomization must be performed at Visit 2 (Month 0).

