### 7.2.3 Patient-Reported Outcomes

The PRO questionnaires are recommended to be completed before any other assessments are performed, by the patient in a quiet place without influence from trial personnel or accompanying family or friends. The trial personnel are not to help the patient choose an answer and must neither interpret nor rephrase questions which patients do not understand.

At visits where the IPSS (Section 7.2.1.3) is to be completed, the IPSS should be completed before the PRO questionnaires. The PRO questionnaires should then be completed in the following order: 1) DASI, 2) CAQ, and 3) EQ-5D-5L.

After completion of the questionnaires, the trial personnel will review the document for completeness only and enter the data into the eCRF. The patient should be given the opportunity to complete the questionnaire if this was not done in the first place, before leaving the site.

The questionnaires are validated for multinational use and will be provided in the local languages, as applicable.

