### **10.3 Use of Patient Reported Outcome Measures Instruments**

An electronic PRO (ePRO) system provided by an independent third-party CRO will be used for collecting PRO measures.

The IPSS, DASI, CAQ, and EQ-5D-5L questionnaires will be collected using an electronic trial slate device to be completed by the patient.

In case of missing assessments, reasons should be recorded by trial personnel in the eCRF: questionnaire not given to the patient, patient refusal, lack of time from patient or functional limitation from patient to complete the questionnaire.

Handling of missing assessments and missing data will be detailed in the SAP.

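### Protocol 6.3 schedules the baseline IPSS, DASI, CAQ and EQ-5D-5L after open-label randomization, so these self-reported baselines can be given with the arm known

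*Protocol*

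**What the plan says.** Protocol 6.3 splits Visit 2 into steps. Before randomization there are only general checks: "Ensure that the patient is still eligible for participation in the trial", and a check of criteria that screening could not fully settle. Randomization follows. A further list must then be done "after randomization, but before administration of the first dose of IMP (degarelix or leuprolide". IPSS is first on that list and DASI, CAQ and EQ-5D-5L are second. Vital signs come later on the same list. Dosing is last.

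Protocol 3.5.3 explains that a double-blind design was judged impractical. Blinding applies to the event adjudicators, for whom coordinators "redact information regarding the open-label trial treatment information for each endpoint". Allocation is made at the site: "The patients will be randomized and allocated to a treatment through the eCRF" (4.2.2).

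Protocol 7.2.3 adds a general recommendation: "The PRO questionnaires are recommended to be completed before any other assessments are performed". It also asks that patients answer without influence from staff or companions. Sections 7.2.1.3, 7.2.3.1 and 7.2.3.2 place the first questionnaires at baseline, Visit 2, and say nothing about randomization.

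On blood pressure, 4.2.2 states: "Only patients who meet the eligibility criteria (Section 4.1) will be randomized to a treatment arm in this trial". Exclusion criterion 4 in 4.1.2, which opens "Uncontrolled hypertension (systolic blood pressure", is tied to the time of randomization. Section 7.2.4.2 makes the Visit 2 reading, with a possible repeat, decide entry.

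**The concern.** A baseline is normally secured before allocation so that it cannot depend on the arm. These four instruments are self-reported symptom, function, anxiety and health-status scores. A patient who has just learned which drug he will receive, in a trial about cardiovascular risk, could answer some items differently. If so, the baseline is no longer a pure pre-treatment covariate: adjusting for it, or subtracting it, can carry an arm difference into the treatment contrast.

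At stake are the IPSS, DASI, CAQ, EQ-5D-5L change and QALY comparisons. The adjudicated MACE analysis and the key secondary endpoints do not use these scores.

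A smaller matter sits in the same section. Blood pressure at Visit 2 is an entry condition, yet the only Visit 2 reading that 6.3 lists comes after randomization.

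**Working it through.** **1. Does any text reverse the order?**
- Protocol 6.3 is the only text that fixes the order relative to randomization, and its list is mandatory.
- Protocol 7.2.3 orders the questionnaires relative to other assessments and is a recommendation. It is compatible with 6.3, where they come first after randomization.
- Table 1 shows one mark at Visit 2. Its footnotes d and e order the questionnaires among themselves only.
- No section delays disclosure of the arm to the patient.

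The baselines can therefore be given with the arm known. How often that happened is not stated.

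**2. Where the baselines are used**
- IPSS (SAP 9.3.12), DASI and CAQ (SAP 9.3.13): the baseline is part of the change score and is also a covariate.
- EQ-5D-5L change from baseline: listed among the other secondary analyses in SAP 9.3.
- QALY (SAP 9.3.11): the baseline index is the starting point of the trapezoid. The model adjusts for treatment, age group and region, with no baseline utility.

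**3. Weight of the baseline in the QALY**

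Under the trapezoidal rule the baseline weight is half the length of the first interval. On nominal days, over 336 days:
- Visit 8 present (Day 168): 168/2 = 84, and 84/336 = 25%. The SAP's additional Month 11 point does not alter this, because only the first interval matters.
- Visit 8 missing, next value at Visit 13 (Day 308): 308/2 = 154, and 154/336 = 46%.
- Visit 8 missing, next value at Visit 14 (Day 336): 336/2 = 168, and 168/336 = 50%.

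**4. How a shift would carry through**

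The documents give no shift, so everything here is assumed. Let d be the between-arm shift in baseline caused by knowing the arm, f the same at follow-up, and r the baseline-to-follow-up correlation (scores in SD units, equal SDs).
- ANCOVA bias: f − r·d as scheduled; f with a pre-randomization baseline.
- QALY bias as a mean index over 336 days, with Visit 8 present: 0.25d + 0.75f as scheduled; 0.75f with a pre-randomization baseline (d and f in index units).

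Illustration for ANCOVA, taking all 545 randomized patients as analysed: SE = √(1 − r²) × 2/√545, and the false-positive rate is P(|Z + bias/SE| > 1.96). With r = 0.5, SE = 0.866 × 0.0857 = 0.0742.

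| Assumed shift | As scheduled | Baseline before randomization |
|---|---|---|
| d = 0.1, f = 0 | bias 0.05 in size, 10.3% | bias 0, 5.0% |
| d = 0.05, f = 0 | bias 0.025 in size, 6.3% | bias 0, 5.0% |
| d = 0.1, f = 0.1 | bias 0.05, 10.3% | bias 0.10, 27.1% |

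For r from 0.3 to 0.7 the first row runs 6.6% to 20.8% against 5.0%. The third row runs 7.8% to 13.7% as scheduled, against 23.1% to 37.3%. For shifts in the same direction, the reorder lowers ANCOVA bias only if f < r·d/2, here 0.025 SD. The table shows that the direction depends on unknown inputs; it does not estimate a bias in this trial.

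**5. Blood pressure, side by side**
- 4.1.2 and 7.2.4.2: the reading at randomization or Visit 2 decides entry. 4.2.2: only eligible patients are randomized.
- 6.3: a general eligibility check comes before randomization; the listed Visit 2 reading comes after it.
- Table 1 footnote g: vital signs before dosing, and Screening results available before randomization. A Visit 1 reading exists (6.2).

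The general check implies a reading before randomization, but no text says when the Visit 2 reading is to be taken.

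**The case against.** The strongest objection is that the reorder is not shown to improve the analyses. Follow-up questionnaires stay open-label for the year whatever is done at Visit 2. If knowing the arm shifts baseline and follow-up alike, the scheduled order partly cancels the bias in the ANCOVA. The algebra above bears this out, and it stands: no lower error rate can be claimed for IPSS, DASI or CAQ. It does not justify keeping a post-allocation baseline, because that means relying on two unknown biases to offset each other. For the QALY, shifts in the same direction add instead of cancelling.

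Second, the mechanism is unproven. Both arms receive active treatment, the questionnaires come first on the list and before any injection, and no text says that the patient is told his arm before answering. This also stands, and it limits the point to a possibility that the schedule permits.

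Third, on blood pressure, the pre-randomization eligibility check and the Visit 1 reading already cover much of the ground. A reader might infer that ineligible patients were randomized and then left undosed, affecting the Full Analysis Set. The documents do not support that: nothing forbids an earlier Visit 2 reading, and 6.3 lets only patients who meet all criteria proceed.

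**Conclusion.** The point holds as a design weakness of modest reach. Protocol 6.3 places four self-reported baselines after open-label randomization, with nothing to keep the arm unknown until they are complete. The only size that follows from the documents is the QALY weight: 25% on nominal days with Visit 8 present, and up to about 50% without it. It measures exposure to a baseline shift, not a bias.

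A reader might go further and conclude that the patient-reported results are biased, or biased in favour of one drug. The documents give neither a shift nor its direction, so that does not follow. The affected endpoints are secondary, outside the fixed-sequence hierarchy, and analysed without multiplicity control. The blood pressure matter is an inconsistency of wording, with no view taken on the limits.

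**What to change.** **Protocol 6.3 (for any reuse of this design).** Move the IPSS, DASI, CAQ and EQ-5D-5L to the steps before randomization at Visit 2. This reorders one visit and adds no visit or procedure. The cost is a few questionnaires from patients who are then not randomized.

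**Data already collected.** SAP section 3 records that the trial was terminated with 545 patients randomized, so the order cannot be changed for them. State in the SAP and the report that the patient-reported baselines were scheduled after open-label randomization. The questionnaires "will be collected using an electronic trial slate device to be completed by the patient" (Protocol 10.3) and allocation runs through the eCRF. If both systems stored times, report by arm how many baselines were completed before and after randomization. The documents do not say that times were kept, and 7.2.3 also describes staff entering the answers into the eCRF, so the count may not be possible. The cost is one sentence and, where feasible, one small table.

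**Blood pressure.** Reconcile the timing of the Visit 2 reading across 4.1.2, 4.2.2, 6.3, Table 1 footnote g and 7.2.4.2. This is an edit to wording only.
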